7.7.4 Analysis of bAb against ZIKV by ELISA Binding Assay

The bAb against ZIKV by ELISA binding assay will be summarized by treatment group and scheduled visit as follows:

- GMC of bAb against ZIKV at Day 1, Day 29, Day 57, Month 7, and Month 13 as measured by ELISA binding assay with corresponding 95% CIs.
- GMC of bAb against ZIKV in initially flavivirus seronegative participants at Day 1, Day 29, Day 57, Month 7, and Month 13 as measured by ELISA binding assay with corresponding 95% CIs.
- GMC of bAb against ZIKV in initially flavivirus seropositive participants at Day 1, Day 29, Day 57, Month 7, and Month 13 as measured by ELISA binding assay with corresponding 95% CIs.
- Percentage of participants who seroconverted from Day 1 (baseline) to Day 29, from Day 1 to Day 57, from Day 1 to Month 7, and from Day 1 to Month 13.
- Proportion of initially seronegative participants with a seroresponse at Day 29, Day 57, Month 7, and Month 13 as measured by ELISA binding assay.
- Proportion of initially seropositive participants with a 2-fold or 4-fold increase in bAb concentration as compared with baseline at Day 29, Day 57, Month 7, and Month 13 as measured by ELISA binding assay.

7.7.5 Analysis of IgG and IgM antibodies against envelope- and NS1- based antigens

The GMC for IgG and IgM antibodies against envelope- and NS1-based antigens present in serum collected at baseline and at end of study measured as antibody binding by ELISA or equivalent methodology to flaviviruses will be summarized by treatment group with corresponding 95% CIs.

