Participants (males and females 18 to 49 years of age, inclusive), will be included in the study if they are in good health as determined by medical history, clinical laboratory assessments, vital sign measurements, a physical examination at screening and per investigator judgement. Negative pregnancy tests will be required at screening and before vaccine administration for female participants of childbearing potential. Flavivirus serostatus (positive or negative) will be determined by ELISA or other commercially available serological assay. The full lists of inclusion and exclusion criteria are provided in Section 3.2.1 and Section 3.2.2, respectively.

Safety Assessments:

Safety assessments will include monitoring and recording of solicited AEs (local and systemic reactogenicity events) and unsolicited AEs, serious AEs (SAEs), AEs of special interest (AESIs), AEs leading to study withdrawal, medically attended AEs (MAAEs); clinical laboratory test results (hematology, serum chemistry, and coagulation); vital sign measurements; and physical examination findings.

Immunogenicity Assessments:

Immunogenicity assessments will include the following:

- Serum neutralizing antibodies (nAb) against ZIKV
- Serum binding antibodies (bAb) against ZIKV

Vaccine, Dosage, and Route of Administration:

mRNA-1893 is a novel lipid nanoparticle (LNP)-encapsulated mRNA-based vaccine encoding the full pre-membrane and envelope (prME) structural polyproteins of ZIKV. mRNA-1893 consists of an mRNA Drug Substance formulated with LNPs. mRNA-1893 is provided as a sterile liquid for injection at a concentration of 0.5 mg/mL in 100 mM Tris buffer, 7% propylene glycol, and 1 mM diethylenetriamine-pentaacetic acid (DTPA).

mRNA-1893 (10, 30, 100, or 250 µg) and placebo will be prepared as outlined in the pharmacy manual and administered via IM injection (0.5 mL) into the deltoid muscle on designated vaccination days. The second dose of vaccine or placebo will be administered preferably in the same arm used for the first dose.

The placebo is 0.9% sodium chloride injection, United States Pharmacopeia (USP) or British Pharmacopeia (BP).

Sample Size:

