3.5.5 Safety Assessments

Safety assessments will include monitoring and recording of solicited AEs (local and systemic reactogenicity events) and unsolicited AEs, SAEs, AESI, AEs leading to study withdrawal, and MAAEs; clinical laboratory test results (hematology, serum chemistry, and coagulation); vital sign measurements; and physical examination findings. If an MAAE occurs that evokes clinical symptomatology consistent with a flavivirus infection, serology and polymerase chain reaction testing against dengue will be uniformly collected.

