- d Serology testing will include hepatitis B virus surface antigen, hepatitis C virus antibody, human immunodeficiency virus type 1 and 2 antibodies.
- ^e Flavivirus screening by ELISA will include screening for dengue, West Nile, and Zika.
- f Urine drug screen will include amphetamines, benzodiazepines, cocaine, methadone, opiates, and phencyclidine (Exclusion Criterion 26, Section 3.2.2).
- g Urine pregnancy testing only for women of childbearing potential (performed at the local laboratory) at the Screening Visit, prior to vaccination administration and as needed at unscheduled visits.
- h Participants are assessed for eligibility/contraindications for second vaccination (Section 3.4.2.3).
- At each vaccination visit (Day 1 and Day 29), study staff will provide a diary card to participants and training on its proper use. The participant will use the diary card (Section 3.5.2) for recording information on solicited AEs (Section 3.5.6) during the 6 days after vaccine administration, unsolicited AEs (Section 3.5.7) during the 28 days after each vaccination.
- At each visit when vaccine injections are administered, participants will be monitored for 60 minutes after vaccine administration; assessments will include vital sign measurements and monitoring for local or systemic reactions.
- ^k For all participants, blood samples for immunogenicity testing will be collected for the analysis of vaccine-induced immunogenicity (Section 3.5.3). At EOS, blood samples will also be used to test for flavivirus seroconversion.
- Sample collection before study vaccination.
- m During the Vaccination Phase, all participants will receive a post-vaccination safety telephone call at 24 hours and 48 hours after vaccinations (Day 2 and Day 3 after first vaccination and Day 30 and Day 31 after second vaccination). Trained site personnel will inquire about the presence of solicited and unsolicited AEs and concomitant medication use and will remind participants to keep their diary cards up to date (Section 3.5.2).
- ⁿ The investigator must report all SAEs, MAAEs, and AESI within 24 hours of awareness (Section 3.5.7.3).

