3.3 Exploratory Objectives

The exploratory objectives of the study are the following:

- 1. To evaluate the immunogenicity of a 2-dose vaccination schedule of mRNA-1893 Zika vaccine, given 28 days apart, as measured by enzyme-linked immunoabsorbent assay (ELISA) and additional neutralization assays.
- 2. To assess the occurrence of flavivirus infection throughout the course of participation in the trial.

4 Study Endpoints

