- Proportion of initially seropositive participants with a 2-fold or 4-fold increase in bAb concentration as compared with baseline as measured by ELISA binding assay
- Immunoglobulin G (IgG) and immunoglobulin M (IgM) antibodies against envelope- and NS1- based antigens present in serum collected at baseline and at end of study measured as antibody binding by ELISA or equivalent methodology to flaviviruses

Study Design

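### SAP 7.7.5 reports only pooled group means for the flavivirus-infection objective, so there is no pre-specified count of infections among mRNA-1893 recipients

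*SAP*

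**What the plan says.** SAP 3.3 and Protocol 2.3 share an exploratory objective: "To assess the occurrence of flavivirus infection throughout the course of participation in the trial". The endpoint that fits it (SAP 4.3, Protocol 3.6.3) is IgG and IgM to two kinds of antigen, envelope and NS1; its text ends "antigens present in serum collected at baseline and at end of study measured as antibody binding by ELISA or equivalent methodology to flaviviruses". It carries no infection definition, cut-off or rate.

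SAP 7.7.5 is the only analysis of that endpoint. It takes "The GMC for IgG and IgM antibodies against envelope- and NS1-based antigens present in serum collected at baseline and at end of study", which "will be summarized by treatment group with corresponding 95% CIs". It does not split by baseline serostatus.

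The protocol expects a result for each participant. Table 5, footnote k: "At EOS, blood samples will also be used to test for flavivirus seroconversion". Protocol 3.5.5 adds that, at medically attended events suggesting flavivirus infection, "serology and polymerase chain reaction testing against dengue will be uniformly collected". The SAP gives no table for either, and SAP 8 does not list the omission as a change.

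The Protocol Synopsis describes the product as an "mRNA-based vaccine encoding the full pre-membrane and envelope (prME) structural polyproteins of ZIKV". NS1 is not described as part of it.

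**The concern.** Occurrence of infection is a yes/no outcome for each participant, and a group geometric mean does not count such outcomes. The SAP does plan participant-level results for its other antibody assays. For PRNT, MN, RVNT and the ZIKV binding ELISA (7.7.2 to 7.7.4) it gives seroconversion percentages and results by baseline serostatus. Section 7.7.5 has neither, yet its objective is the one that needs a count.

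The envelope component has a second problem. A prME vaccine is meant to raise antibody to ZIKV envelope, so a higher envelope mean at end of study in an mRNA-1893 group is expected without any infection. The SAP does not say which antigen is to be read as evidence of infection.

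At stake is whether the objective can be answered among vaccinees. A lesser matter is that Protocol 1.6 reads Month 7 and Month 13 titres as persistence, and no planned output marks participants who may have been infected in between.

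**Working it through.** **Inputs from the documents.** There are 24 participants per mRNA-1893 dose group, 4 of them seropositive at baseline, and 4 × 6 = 24 pooled placebo recipients (Table 1 in both documents). Percentages get Clopper-Pearson intervals, and geometric means get t-based intervals on the log scale (SAP 7.1).

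**The plan's own figure.** The only design figure is the chance of seeing at least one AE among 24. It reproduces: 1 − 0.90^24 = 92.0% and 1 − 0.95^24 = 70.8%. There is no corresponding figure for infection, and the documents give no attack rate, fold rise or assay SD. Those values are assumed below.

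**Step 1: can a count be recovered from the mean?** If x of 24 participants rise k-fold and the rest do not change, the GMC is multiplied by k^(x/24).
- One participant with a 64-fold rise: 64^(1/24) = 1.189.
- Three participants with 4-fold rises: 4^(3/24) = 1.189.

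The ratios are identical because 4³ = 64. One infection and three infections give the same summary. This step needs no assumption about the SD.

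**Step 2: how far does one infection move the mean?** For one participant in 24:
- 4-fold rise: 4^(1/24) = 1.06
- 16-fold rise: 16^(1/24) = 1.12
- 64-fold rise: 64^(1/24) = 1.19

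**Step 3: how wide is the interval?** The 95% CI factor is 10^(t × SD/√24), with t(0.975, 23 df) = 2.069.
- SD 0.2 log10: 1.22
- SD 0.4 log10: 1.48
- SD 0.6 log10: 1.79

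Across these ranges a single infection stays inside the interval.

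**Step 4: two large rises.** Two of 24 with 50-fold rises give 50^(2/24) = 1.39, or 0.1416 on the log10 scale. This is inside the interval only if SD > 0.1416 × √24 / 2.069 = 0.335 log10. Below that SD the shift is larger than the CI factor, so masking depends on the assay. Large rises in a few participants would also widen the end-of-study spread, which these assumed SDs leave out.

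**Step 5: what a count would show.** Using the SAP's own interval method with illustrative counts:
- 0/24: 0% (0 to 14.2%)
- 1/24: 4.2% (0.1 to 21.1%)
- 2/24: 8.3% (1.0 to 27.0%)
- 3/24: 12.5% (2.7 to 32.4%)

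The intervals are wide, but the counts in Step 1 that share one GMC ratio become distinguishable.

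**The case against.** The strongest reply is that the trial is not blind to infection. ZIKV seroconversion percentages are planned by treatment group at Month 7 and Month 13, and placebo is one of the groups. Placebo recipients receive no antigen, so seroconversion among those 24 reflects natural exposure or assay noise. All immunogenicity values are listed (SAP 7.7.1), so paired results can be read for each person. Dengue testing is collected at suggestive medically attended events. The objective is also the second of two exploratory ones, and its link to this endpoint is inferred because the documents do not map endpoints to objectives.

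Much of this stands. A reader might infer that the trial would yield no infection information at all, and these sources show otherwise. They remain partial. The placebo percentages are ZIKV-based and do not cover vaccinees, a listing without a pre-set rule leaves infection to be defined after the fact, and dengue testing reaches only symptomatic cases. The inferred link is reasonable, because in vaccinees the other antibody endpoints measure response to the vaccine.

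Two other strong readings are also unsupported.
- A reader might infer that persistence cannot be separated from natural boosting. Placebo recipients are followed to Month 13 with the same titres, which gives a group-level check, though a weak one at n = 24. With no attack rate in the documents, material distortion of late titres is not shown.
- A reader might infer that infections always vanish inside the confidence interval. Step 4 shows that this depends on the SD.

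The envelope problem applies to mRNA-1893 recipients, not to placebo.

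**Conclusion.** The point holds in a limited form. Followed exactly, SAP 7.7.5 leaves the infection objective without a pre-specified count or rate among vaccinees, because a pooled GMC does not determine how many were infected and its envelope part is expected to rise with vaccination. That conclusion rests on the documents and on Step 1 alone. The sizes in Steps 2 to 4 rest on assumed fold rises (4 to 64, and 50) and assumed SDs (0.2 to 0.6 log10), and serve as illustration.

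The documents support saying that envelope is encoded and that NS1 is not described as encoded. They give no cut-off or cross-reactivity data for NS1, so they do not establish how well it would separate infection from vaccination. No primary or secondary conclusion, escalation step or pause rule depends on this. It is a cheap improvement.

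**What to change.** In SAP 7.7.5:
- Add the number and percentage of participants with NS1-based seroconversion from baseline to end of study, by treatment group and baseline serostatus, with Clopper-Pearson intervals.
- Use the rule that SAP 4.3 already applies to ZIKV binding antibody (below LLOQ to at or above LLOQ, or at least a 4-fold rise), unless assay validation supports another cut-off. Fix the cut-off before the end-of-study data are unblinded.
- List dengue-confirmed medically attended cases alongside the count.
- State that envelope antibody is not used as an infection marker in mRNA-1893 recipients.
- Flag NS1 seroconverters in the Month 7 and Month 13 titre listings.

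The cost is SAP wording, one table and a listing flag; the samples and assays are already planned. The downside is that the NS1 cut-off may misclassify some participants through flavivirus cross-reactivity, especially those seropositive at baseline. Showing the result by serostatus keeps that visible.

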7.8 Interim Analyses

Once all participants from a cohort have completed the Vaccination Phase through Visit 9, the database will be locked for that cohort and safety and immune test results will be analyzed through 28 days following the second vaccination by an unblinded statistician. As dose escalation occurs, cumulative analyses will be included for each subsequent data lock

Protocol mRNA-1893-P101

to allow for all prior dosing cohorts to be analyzed by dose assignment, and in aggregate for mRNA-1893 exposure. Immunogenicity and safety data will be summarized for each treatment group, including summarization of change from baseline in each group where applicable.

8 Changes and Clarifications from Planned Analyses in Protocol

The following changes were made to the planned analyses:

- In protocol section 3.6.5, the All Enrolled Participants Set was defined as including all participants who signed the ICF. The definition has been changed to: The All Enrolled Participants Set will include all participants who signed the ICF and did not screen fail.
- In protocol section 3.6.6.2, it indicates that "the difference in the proportion of participants with AEs will be provided, comparing each dose level with placebo pooled across all cohorts." The actual difference will not be computed. The proportions for each dose level and pooled placebo will be presented and is considered sufficient for comparison.

9 References

Department of Health and Human Services (DHHS), National Institutes of Health, National Institute of Allergy and Infectious Diseases, Division of AIDS. Division of AIDS (DAIDS) table for grading the severity of adult and pediatric adverse events. Version 2.0. November 2014. [cited 2019 April 13]. Available from:

https://rsc.niaid.nih.gov/sites/default/files/daids-ae-grading-table-v2-nov2014-highlightedchanges.pdf.

Protocol mRNA-1893-P101 Date Issued: 25May2021

10 List of Appendices

10.1 Appendix A Analysis Visit Windows for Safety and Immunogenicity Analysis

Table 3 Visit Window Mapping Rules

| Table 3 Visit Window Mapping Rules | | |
|---------------------------------------|--|----------------------------|
| Labs (Hem | atology, Chemistry, and Coagulation) and | l Vital Signs |
| Visit | Target Study Day | Visit Window |
| Day 1 | Date of First Vaccination (1) | Pre-dose |
| Day 1, 1 hour postdose – Vitals only | 1 | ≥ 1 hour post-dose |
| Day 8 - Labs only | 8 | [8,11] |
| Day 29 | Date of Second Vaccination (29) | [29,36] |
| Day 29, 1 hour postdose – Vitals only | 29 | ≥ 1 hour post-dose |
| Day 36 - Labs only | 36 | [36,39] |
| Day 57 (Month 2) – Labs only | 57 | [50,64] |
| | Adverse Events | |
| Stage | Vaccination | Target Time Frame |
| Vaccination | All | [1, 57] |
| Short-Term Follow-up | First | [1,29] |
| | Second | [29,57] |
| Long-Term Follow-up | First | NA |
| | Second | [57, Month 12 Safety Call] |
| Overall | All | [1, Month 12 Safety Call] |

Protocol mRNA-1893-P101

| Immunogenicity | | | | | |
|-------------------------------------|-------------------------------|------------|--|--|--|
| Visit Target Study Day Visit Window | | | | | |
| Day 1 | Date of First Vaccination (1) | Pre-dose | | | |
| Day 29 | 29 | [29,36] | | | |
| Day 57 (Month 2) | 57 | [50,64] | | | |
| Month 7 | 196 | [182,210] | | | |
| Month 13 | 364 | [343, 385] | | | |

Protocol mRNA-1893-P101

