Participants will record on the same diary card daily any unsolicited AEs experienced, daily body temperature, and concomitant medications and vaccinations (excluding vitamins and minerals) received from 7 through 28 days after each vaccination. Participants will be instructed to return the completed diary card to the Investigator at Day 29 and Day 57.

All concomitant medications and vaccinations (excluding vitamins and minerals) received and SAEs, MAAEs, AESIs, and

AEs leading to withdrawal from vaccine dosing or from the study will be collected from Day 1 until Month 13 (EOS Visit). Other safety assessments will include clinical laboratory test results (hematology, serum chemistry, and coagulation); vital sign measurements; and physical examination findings. Blood samples for immunogenicity assessments will be collected the day of each vaccination (Days 1 and 29 before vaccination), 28 (+14) days after each vaccination, and during the Long-Term Follow-up Phase at Month 7 (\pm 14 days) and Month 13 (\pm 14 days).

Once all subjects from a cohort have completed the Vaccination Phase through Day 57 (-7/+14 days), the database will be locked for that cohort and safety and immunogenicity data will be analyzed through 28 days following the second vaccination by an unblinded statistician. As dose escalation occurs, cumulative analyses will be included for each subsequent data lock to allow for all prior dosing cohorts to be analyzed by dose assignment, and in aggregate for mRNA-1893 exposure. Immunogenicity and safety data, including mean group analyses of change from baseline, where applicable, will be summarized for each dose group. These data are required to inform decisions on dose selection for this and other development programs using the same messenger RNA (mRNA) platform.

When all participants have completed their final contact (approximately 12 months after the last vaccination), immunogenicity testing is completed, and all queries resolved, the database will be locked and analyzed with a final clinical study report.

Study Population:

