3.6.8 Interim Analyses

Once all subjects from a cohort have completed the Vaccination Phase through Visit 9, the database will be locked for that cohort and safety and immune test results will be analyzed through 28 days following the second vaccination by an unblinded statistician. As dose escalation occurs, cumulative analyses will be included for each subsequent data lock to allow for all prior dosing cohorts to be analyzed by dose assignment, and in aggregate for mRNA-1893 exposure. Immunogenicity and safety data, including mean group analyses of change from baseline, where applicable, will be summarized for each dose group. These data are required to inform decisions on dose selection for this and other development programs using the same mRNA platform. Participant-level dose assignment will not be released to the participants or to those individuals involved directly in managing or assessing safety until the study is completed.

Additional information can be found in the statistical analysis plan.

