6.2.1 Intent-to-Treat Immunogenicity Set

The ITT set consists of all participants who were randomized to the study, regardless of protocol violations, unacceptable visit windows, missed vaccination, or missing data.

The ITT set will be used for supportive analyses at the final analysis only. If the ITT set differs from the overall PP set by more than 10% (ie, the difference between the number of participants in the ITT set and the number of participants in the overall PP set divided by the number of participants in the PP set is greater than 10%), then the primary immunogenicity analyses will also be conducted at the final analysis using the ITT set.

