6.2.2 Per-Protocol Sets

The PP sets for analysis of immunogenicity data will be defined for each visit (ie, Visit 1 - Day 1, Visit 5 - Day 29, Visit 9 - Day 57 [Month 2], Visit 14 - Month 7, Visit 20 - Month 13 [EOS] PP sets) and consist of all participants who meet the following criteria:

- Did not have a major protocol deviation
- Received vaccine within the acceptable vaccination window and received full dose[s] of assigned vaccine
- Had immunogenicity samples taken within acceptable visit windows
- Had a pre-vaccination and the corresponding 1 post-vaccination serum sample available for testing. For the Visit 1 – Day 1 PP set, participants will only be required to have a pre-vaccination serum sample available for testing

Protocol mRNA-1893-P101

Participants who miss the second vaccination may still be included in the PP set for Visit 5 immunogenicity data analysis. If the second vaccination occurs outside of the window, the subsequent data may need to be excluded from the PP set for visits occurring after the second vaccination.

In addition, an overall PP set will be defined for modeling across visits. A participant who is included in any one of the per-visit PP sets will be included in the overall PP set.

The PP sets will be used for the primary immunogenicity analyses at each interim analysis and at the final analysis.

7 Statistical Analysis

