- Study Day on or after the date of the first vaccination but before the second vaccination (if applicable) will be calculated as: date of assessment/event date of the first vaccination + 1;
- Study Day after the date of the second vaccination will be calculated as: date of assessment/event date of the second vaccination + 1; if Study Day is on the same day as the second vaccination, date and time will be compared with the second vaccination date and time. If it is prior to the second vaccination, then study Day is calculated as: date of assessment/event date of the first vaccination + 1; If it is after the second vaccination then Study Day is calculated as: date of assessment/event date of the second vaccination + 1.

For GMT calculation, antibody values reported as below LLOQ will be replaced by $0.5 \times LLOQ$. Values that are greater than the upper limit of quantification (ULOQ) will be converted to the ULOQ. Missing results will not be imputed.

Date Issued: 25May2021

The following timeframes will be defined for reporting safety data in this study:

- Vaccination: First vaccination on Day 1 to 28 days after last vaccination. If a participant receives two vaccinations, this stage starts at the first vaccination on Day 1 and continues through the 28th Day after the 2nd vaccination.
- Within 28 days of vaccination: Consists of all periods that begin with a vaccination and continue through the 28th Day after the vaccination. This is a subset of the vaccination stage. If a participant receives two vaccinations, this stage includes the two 28-Day periods that begin after each vaccination.
- Overall: Begins at the first vaccination on Day 1 and continues through the final safety call.

Analysis sets for the various analyses are defined in Section 6.

The 95% confidence interval (CI) for percentage will be obtained from SAS procedure of Proc Freq using Clopper-Pearson method. The 95% CI for GMT will be calculated based on the t-distribution of the log-transformed values then back transformed to the original scale for presentation.

Expected visit windows for all study assessments are detailed in Appendix A.

All analyses will be conducted using SAS Version 9.4 or higher.

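### SAP Table 3 keeps Day 29 and Day 57 windows narrower than protocol V3.0 allows and does not say from which dose its days are counted

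*SAP*

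**What the plan says.** Protocol V3.0 (17 March 2020) gives dose 2 as Day 29 (+14 days) in Sections 3.1 and 3.4.2.1, so Days 29-43. Its Table 5 allows +3 days for the Day 36 visit and -7/+14 days for the Day 57 visit. The Synopsis agrees on the latter: "Vaccination Phase through Day 57 (-7/+14 days"). Labs are due 7 days after vaccination (Section 3.5.8). Sections 1.6 and 3.1 place the later titre sample 28 (+14) days after each vaccination.

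SAP V3.0 (May 2021) still names protocol V2.0 as its basis (Section 2) and still gives dose 2 as Day 29 (+7 days) (Section 5.1). Table 3 in Appendix A maps Day 29 labs, vital signs and titres to [29,36]. It maps the 7-day post-dose-2 labs by "Day 36 - Labs only | 36 | [36,39"], and titres by "Day 57 (Month 2) | 57 | [50,64"], with the same range for Day 57 labs. The SAP's document history for V3.0 records one change to these windows, in the Month 13 row.

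SAP Section 7.1 says "Expected visit windows for all study assessments are detailed in Appendix A". Section 6.2.2 makes it a condition of the Per-Protocol Sets that the participant "Had immunogenicity samples taken within acceptable visit windows", without naming the table or document that defines those windows.

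**The concern.** A visit-mapping table should hold every visit that the protocol counts as on time. This one has upper limits that protocol V3.0 has overtaken. Its post-dose-2 rows also appear to be fixed relative to dose 1, while the visits themselves move with dose 2. A participant dosed late but within the rules could then have correctly timed results that map to no visit or to the wrong one.

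Two things are at stake. The first is the by-visit summaries of labs and titres. The second is conditional: if Table 3 supplies the Per-Protocol windows, the Day 57 PRNT titres, a secondary endpoint, can leave the analysis set used at each cohort's interim. Of that interim the protocol says "These data are required to inform decisions on dose selection for this and other development programs".

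The intent-to-treat set would not compensate there: "The ITT set will be used for supportive analyses at the final analysis only". The 10% rule for repeating the immunogenicity analyses on that set compares it with the overall Per-Protocol Set, and "A participant who is included in any one of the per-visit PP sets will be included in the overall PP set". Losses confined to Day 57 would therefore not trigger it.

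**Working it through.** **1. Reproduce Table 3.** Counted from dose 1, 29 to 29+7 = [29,36], 36 to 36+3 = [36,39], and 57-7 to 57+7 = [50,64]. All three match. SAP 7.1 also defines a study day from the most recent vaccination, with the day of dose 2 as Day 1. On that count the 7-day lab has target 36-29+1 = 8 and the 28-day sample 57-29+1 = 29, so the printed targets of 36 and 57 do not fit.

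**2. Apply the protocol V3.0 allowances to the same targets.** Day 29 becomes [29,43], Day 57 becomes [50,71], and Day 36 stays [36,39]. Two gaps do not depend on the anchor:
- Pre-dose-2 records on Days 37-43 are outside [29,36]. Both SAP 7.1 definitions count a record taken before dose 2 from dose 1.
- With dose 2 exactly on Day 29, allowed Day 57 samples on Days 65-71 are outside [50,64]. Counting from dose 1 and using nominal schedule days give the same numbers here. Counted from dose 2 they are Days 37-43, also outside.

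**3. Move dose 2 to Day d (29 to 43), counting from dose 1.** The 7-day (+3) lab is on Days d+7 to d+10. The on-target titre is on Day d+28. The allowed titre days are d+21 to d+42 under -7/+14 (22 days), or d+28 to d+42 under 28 (+14) (15 days).

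| d | Lab days | Lab days in [36,39] | On-target titre | -7/+14 days in [50,64] | 28 (+14) days in [50,64] |
|---|---|---|---|---|---|
| 29 | 36-39 | 4 of 4 | 57 | 15 of 22 | 8 of 15 |
| 32 | 39-42 | 1 of 4 | 60 | 12 of 22 | 5 of 15 |
| 33 | 40-43 | 0 of 4 | 61 | 11 of 22 | 4 of 15 |
| 36 | 43-46 | 0 of 4 | 64 | 8 of 22 | 1 of 15 |
| 37 | 44-47 | 0 of 4 | 65 | 7 of 22 | 0 of 15 |
| 43 | 50-53 | 0 of 4 | 71 | 1 of 22 | 0 of 15 |

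The lab misses Day 36 for every d from 33. Days 33-36 lie inside the SAP's own +7 allowance, so the later protocol is not the only cause. For d = 33 to 39 all lab days lie in Days 40-49, which belong to no window. At d = 43 all four fall in the Day 57 window. The on-target titre passes Day 64 from d = 37. These are counts of calendar days, not probabilities.

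**4. Month 7 and Month 13.** Table 3 gives targets 196 and 364 with windows [182,210] and [343,385]. Protocol Table 5 allows ±14. With dose 2 on Day 43 and visits timed from dose 2, the targets become 196+14 = 210 and 364+14 = 378. The ranges are Days 196-224 and 364-392, which pass the upper limits of 210 and 385.

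**5. Cost of one lost titre, if exclusion occurs.** The half-width of the 95% CI on the log scale is proportional to t(0.975, n-1)/√n at a given SD. With the planned group sizes in Table 1 of either document:
- Seropositive dose group, 4 to 3: 2.484/1.591 = 1.56, or 56% wider.
- Seronegative dose group, 20 to 19: 3.0% wider.
- Whole dose group, 24 to 23: 2.4% wider.

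**6. Check the proposed windows.** Counted from dose 2 as Day 1, the lab falls on relative Days 8-11 and the Day 57 visit on relative Days 22-43, whatever d is. Every allowed visit is held for d = 29 to 43. The 28 (+14) wording gives relative Days 29-43, which lie inside. Widening the dose-1 ranges alone would not repair the Day 36 row.

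**The case against.** The best reply is that the days are nominal schedule labels, with Day 29 meaning whenever dose 2 was given. Table 3 supports this in part. Its target for Day 29 labs and vital signs is the date of the second vaccination, and its adverse-event rows run [1,29] and [29,57], while Section 7.1 ties those periods to each vaccination. Section 6.1.3 likewise equates the 7 days after dose 2 with Days 29 to 36. Read this way, the late-dose-2 failures in step 3 disappear. The reply stands to that extent: the dose-1 anchor is an inference. The nominal reading is not clean either, because a range of [29,36] for the dose-2 visit would then have no purpose, and it leaves Days 65-71 outside.

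Second, a reader might infer that late-dosed participants will be excluded from the Day 57 Per-Protocol analysis and their titres lost. The documents do not support that. Section 6.2.2 does not point to Appendix A, Section 7.1 calls those windows expected, and the summaries are by scheduled visit. The rule in Section 2 that the SAP prevails concerns differing analysis methods and does not settle which windows Section 6.2.2 means. Exclusion is possible, not stated.

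Third, a per-protocol window may deliberately be tighter than a conduct window relaxed for COVID-19. That is legitimate, but SAP Section 8, which lists changes from the protocol's planned analyses, records no such choice, and the SAP's citation of protocol V2.0 and +7 days points to an update that was not made.

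**Conclusion.** The point holds as a mismatch between the two documents plus an unstated anchor. That the Day 29 and Day 57 upper limits are shorter than protocol V3.0 allows does not depend on interpretation. The failure of the Day 36 row from dose-2 Day 33, and of the on-target Day 57 titre from dose-2 Day 37, rests on counting from dose 1. That is the best fit to the lab and titre numbers but is not stated. Loss from the Day 57 Per-Protocol PRNT analysis rests on the further assumption that Table 3 supplies the windows meant in SAP 6.2.2. The SAP also gives no rule for results that map to no window.

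The documents do not say how many participants received dose 2 late, so no count can be given. The cost of an exclusion would be small for a full dose group and large only in the seropositive groups of 4, which are imprecise already. A reader should not infer damage to the main safety results. Under SAP 7.6.3 the listings, the shifts to the worst post-vaccination grade and the Grade 2 or higher incidence through 7 days after any vaccination do not depend on these by-visit ranges. The lab consequence is limited to by-visit summaries. The correction is cheap and should be made.

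**What to change.** - In SAP Table 3, state the anchor. Define post-dose-2 windows by the Section 7.1 study day relative to the second vaccination (dose-2 day = 1): Day 36 labs on relative Days 8-11, Day 57 labs and titres on relative Days 22-43.
- Define the Day 29 lab and titre rows as the pre-dose-2 record on Days 29-43.
- Keep the count from dose 1 for participants who do not receive dose 2.
- Check the Month 7 and Month 13 rows by the same rule.
- In SAP 6.2.2, state which windows are acceptable for the Per-Protocol Sets. If a narrower window than protocol Table 5 is wanted there, state it and list it in Section 8.
- Update the protocol version in SAP Section 2 and the +7-day text in Section 5.1.

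The cost is five table rows (Day 29, Day 36 and Day 57 labs; Day 29 and Day 57 titres), two further rows to check, one cross-reference and two text updates. No extra participants, visits or samples are needed.
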